3. SUMMARY OF STUDY PLAN

This is a Phase II randomized, placebo-controlled, double-blind trial of PROSTVAC® in patients with clinically localized prostate cancer undergoing active surveillance. We plan to recruit men with a diagnosis of localized prostate cancer who are being monitored by active surveillance. Detailed inclusion and exclusion criteria are listed in sections 4.1 and 4.2.

Participants will undergo a screening evaluation in which the informed consent form and medical records and tissue release form will be signed in order to obtain information from urologic assessment, biopsy pathology reports, PSA test results, and biopsy tissues. Participants will undergo a brief physical exam and be evaluated for concomitant medications, medical history and baseline symptoms and signs. International Prostate Symptom Score (IPSS) will be obtained. Blood will be collected for complete blood count with differentiation (CBC-diff), comprehensive metabolic panel (CMP), and PSA. Screening visit procedures, including PSA, performed within 90 days prior to the Baseline Visit (first vaccine injection), may be applied toward eligibility.

Participants will also undergo a digital rectal exam (DRE) to confirm clinical stage at screening, if a DRE has not been performed within 180 days before the Baseline Visit.

Following the screening evaluation, eligible participants will be randomized 2:1 to receive PROSTVAC® or placebo. Randomization will be stratified according to the study site and the number of repeat biopsies following diagnosis (≤ 2, or >2). We plan to randomize 150 eligible men (i.e., 100 receiving PROSTVAC® and 50 receiving placebo).

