Following randomization, participants will return for the Baseline Visit and be evaluated for weight, vital signs, AEs and concomitant medications. Blood will be collected for isolation of peripheral blood mononuclear cells (PBMC). Blood will also be collected for PSA and for serum soluble antibodies to tumor-specific antigens. Blood will be collected prior to administration of the vaccine injection. Participants will receive a priming vaccination with subcutaneous injection of PROSTVAC-V or placebo, injected into the upper outer thigh or upper arm. Participants will be provided with instructions for caring for injection site. Participants will be instructed to record adverse events and concomitant medications throughout the intervention. Participants will be reminded to avoid close contact or household contact with the following high-risk individuals for three weeks after the Day 1 vaccination or until the vaccination site heals completely: (a) children ≤ 3 years of age, (b) pregnant or nursing women, (c) individuals with prior or concurrent extensive eczema or other eczematoid skin disorders, (d) individuals with other acute, chronic, or exfoliative skin condition, or (e) immunocompromised or immunosuppressed persons (by disease or therapy).

On Day 14, 28, 56, 84, 112, 140 following the baseline visit, participants will return for booster vaccinations with subcutaneous injection of PROSTVAC-F or placebo injected into the upper outer thigh or upper arm. It is recommended to alternate the injection sites. Other evaluations at each visit include weight, vital signs, AEs and concomitant medications. At the Day 84 visit International Prostate Symptom Score will be obtained, blood will be collected for PSA and for CBC-diff and CMP. CMP and CBC test results will be evaluated prior to administering the scheduled vaccine to determine whether the injection should be given or omitted. If needed, the labs can be done on a different day prior to the day of the scheduled vaccine injection, but the labs and the vaccine injection should fall within the window specified on the schedule of events.

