7. CLINICAL EVALUATIONS AND PROCEDURES

7.1 Schedule of Events

Evaluation/ Procedure	Pre-Intervention ⁴		Intervention							Post Intervention (7-14 days after the last vaccine dose)	Safety Follow-Up ¹⁰	6-Month Follow-up Visit ^{11,13}
	Screening Visit	Randomization	Baseline Visit (Day 0)	Day 14 (±5)	Day 28 (±7)	Day 56 (±7)	Day 84 (±7)	Day 112 (±7)	Day 140 (±7)			
Informed Consent	X											
Assess Eligibility	X											
Medical History ¹	X											X
Vital Signs, Height ² and Weight	X		X	X	X	X	X	X	X	X		
Karnofsky performance status assessment	X											
Baseline signs and symptoms	X											
International Prostate Symptom Score (IPSS)	X						X			X		X
Digital rectal exam	X ⁵									X ⁶		X ⁶
Blood for CBC-diff, CMP ³	X						X ⁹			X		
Randomization		X										
Blood for PSA	X		X				X			X		X
Blood for PBMCs			X							X		
Blood for serum			X							X		
Release of Agent from Research Pharmacy			X	X	X	X	X	X	X			
Subcutaneous PROSTVAC-V or Placebo Injection			X									
Subcutaneous PROSTVAC-F or Placebo Injection ⁷				X	X	X	X	X	X			
Active Surveillance Status												X
Concomitant Medications	X		X	X	X	X	X	X	X	X		
Adverse Events			X	X	X	X	X	X	X		X	
Post-Intervention Prostate biopsy										X		
Request prostate biopsy reports	X									X		
Request prostate MRI reports ¹²	X											X
Telephone/email Contact ⁸									X		X	X

¹Includes history of autoimmune disease

²Height required at Screening only

³CMP includes serum glucose, urea nitrogen, creatinine, sodium, potassium, chloride, bicarbonate, total protein, albumin, calcium, alkaline phosphatase, ALT, AST, total bilirubin.

⁴Screening visit Evaluation/Procedures performed within 90 days prior to the Baseline Visit (first vaccine injection) can be applied toward Screening/Eligibility evaluation.

⁵Digital rectal exam performed within 180 days prior to the Baseline Visit can be applied toward Screening/Eligibility evaluation.

⁶Performed at the discretion of the individual urologist.

⁷Vaccine injection may be omitted due to adverse events (see section 5.6).

⁸Participants will be contacted (by phone or email) periodically for evaluation of safety or changes in concomitant medications and to be reminded of 6-month follow-up visit.

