7.2 Baseline Testing/Prestudy Evaluation

Participants will undergo a screening evaluation in which the informed consent form and medical records and tissue release form will be signed in order to obtain information from urologic assessment, biopsy pathology reports, PSA test results, and biopsy tissues. Participants will be interviewed for past medical history (including autoimmune disease) and concomitant medication use; and assessed for height, weight and vital signs (temperature, pulse, and blood pressure) and Karnofsky performance status. Subjects will be evaluated for baseline signs and symptoms. International Prostate Symptom Score will be obtained. Blood will be collected for complete blood count with differentiation (CBC-diff), comprehensive metabolic panel (CMP), and PSA. Evaluation/procedures performed within 90 days prior to the Baseline Visit can be applied toward Screening/Eligibility evaluation.

Participants will also undergo a digital rectal exam to confirm clinical stage at screening. A DRE performed within 180 days prior to the Baseline Visit can be applied toward Screening/Eligibility evaluation.

Following the screening evaluation, eligible participants will be randomized 2:1 to receive PROSTVAC® or placebo. Randomization will be stratified by the study site and the number of repeat biopsies following diagnosis (≤ 2 , or >2). The institutional code and the number of repeat biopsies following diagnosis for eligible participants will be captured on the registration CRF and submitted to the University of Arizona Early Phase Chemoprevention Consortium Office for randomization.

CRF Submission Information:

University of Arizona Early Phase Chemoprevention Consortium Office
Attn: [name]
[name]
[name]
[contact]
[contact]
Email: [contact]

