7.3 Evaluation During Study Intervention

Following randomization, participants will return for a Baseline Visit and be evaluated for weight, vital signs, AEs and concomitant medications. Blood will be collected prior to administration of the vaccine injection and shipped overnight at ambient temperature to a central laboratory (see section 10.3) for peripheral blood mononuclear cells (PBMC) isolation. Blood will also be collected for PSA, performed as part of standard of care, and for serum soluble antibodies to tumor-specific antigens.

Participants will receive a priming vaccination with subcutaneous injection of PROSTVAC-V or placebo administered into the upper thigh. Because of the potential of shedding virus at the injection site and the potential of transmission of the vaccinia virus used in the priming vaccine, the injection site will be protected by gauze pads. Participants will be given instructions regarding care of vaccination site and necessary precautions regarding vulnerable populations and also supplies for taking care of the injection site and for disposing of used bandages. Participants will be reminded to avoid close contact or household contact with the following high-risk individuals for three weeks after the Day 1 vaccination or until the vaccination site heals completely: (a) children ≤ 3 years of age, (b) pregnant or nursing women, (c) individuals with prior or concurrent extensive eczema or other eczematoid skin disorders, (d) individuals with other acute, chronic, or exfoliative skin condition, or (e) immunocompromised or immunosuppressed persons (by disease or therapy).

Participants will be instructed to record adverse events and concomitant medications throughout the intervention. Participants will be contacted (by phone or email) periodically throughout the intervention for evaluation of safety, changes in concomitant medications, and to address questions or concerns of the

participant. AEs or new concomitant medications reported at this time will be reported on the appropriate CRF.

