On 14, 28, 56, 84, 112, 140 days following the Baseline Visit, participants will return for interim study visits. Participants will receive booster vaccinations with subcutaneous injection of PROSTVAC-F or placebo, injected into the upper outer thigh or upper arm. It is recommended to alternate the injection sites. Prior to the first booster injection, participants will be evaluated for evidence of bacterial infection, blisters, vesicles or evidence of persistent infection. Weight, vital signs, AEs and conmed information will be collected at each interim visit. At the Day 84 visit, International Prostate Symptom Score will be obtained and blood will be drawn for PSA, CBC-diff, and CMP prior to administration of the vaccine injection. CBC-diff and CMP will need to be evaluated to determine whether the injection on that day may be given or omitted and whether there is the need to repeat safety labs before the next scheduled injection. If needed, the labs can be done on a different day prior to the day for the vaccine injection, but the labs and the vaccine injection should fall within the window specified on the schedule of events. The Day 14 visit can be scheduled +/- 5 days. The Day 28, 56, 84, 112, 140 interim visits can be scheduled +/- 7 days. The vaccine injection may be omitted due to adverse events (as described in section 5.6).

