 - 8.2.9 To determine the safety and feasibility of PROSTVAC® in patients with clinically localized prostate cancer undergoing active surveillance.
 - 8.2.10 To assess the change in circulating 15-Mer PSA-specific T cells.
 - 8.2.11 To assess the change in soluble antibodies to tumor-associated antigens.
 - 8.2.12 To assess the immunologic effects of PROSTVAC® on the target organ using multiplex immunofluorescence.
 - 8.2.13 To assess the effects of PROSTVAC on LUTS by evaluating changes in International Prostate Symptom Score from baseline to 6 months (5-7 months) post-intervention.

If feasible, change in tumor grade and extent will be assessed by central pathology review.

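### The LUTS endpoint (IPSS change from baseline) rests on a single screening score that may be 90 days old; a second score at the Baseline Visit and a baseline-adjusted analysis would make it more precise at little cost

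*Combined protocol and SAP*

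**What the plan says.** Section 8.2.13 defines the LUTS endpoint "by evaluating changes in International Prostate Symptom Score from baseline to 6 months (5-7 months) post-intervention". It does not say which IPSS counts as baseline.

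The IPSS row of the Schedule of Events (7.1) marks four time points: Screening, Day 84, Post Intervention and the 6-month follow-up. The Baseline Visit (Day 0) cell is empty. The text agrees with the table:

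- At screening, section 3 states "International Prostate Symptom Score (IPSS) will be obtained", and section 7.2 repeats it.
- For the Baseline Visit, section 7.3 states "Following randomization, participants will return for a Baseline Visit and be evaluated for weight, vital signs, AEs and concomitant medications", and then lists blood draws and the priming injection. Section 3 describes the visit in the same way. Neither mentions IPSS.
- The next score comes after treatment has started: "At the Day 84 visit, International Prostate Symptom Score will be obtained and blood will be drawn for PSA, CBC-diff, and CMP" (7.3).

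On the age of the screening score, section 7.2 allows: "Evaluation/procedures performed within 90 days prior to the Baseline Visit can be applied toward Screening/Eligibility evaluation". Section 3 and footnote 4 of the schedule give the same 90 days.

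Section 13.5 plans a two-sided two-sample t test at 5% for each secondary endpoint, states no covariate adjustment, and calls these analyses exploratory.

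**The concern.** Each man has one pre-treatment IPSS. In an unadjusted comparison of change scores, all the error in that score passes into his change, and the change is counted from a date that can be three months before the first injection. The Baseline Visit is attended before the first injection and already includes assessments and blood draws, so a second score could be had there for one extra form.

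What is at stake is the precision of the LUTS comparison (objective 1.2.13). IPSS is the only scored patient-reported urinary measure in the trial. A noisier comparison is less able to show a modest worsening of symptoms, or to rule one out.

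**Working it through.** **The plan's own figures.** No power or precision figure is given for IPSS. The only power figure is for the CD8/CD4 endpoints (section 13.4: at least 90% at d = 0.63, 63 v 31 men, 2.5% two-sided, PROSTVAC SD twice the placebo SD). It reproduces with placebo SD 1 and PROSTVAC SD 2. The pooled SD is √[(62×4 + 30×1)/92] = 1.738, the difference 0.63 × 1.738 = 1.095, and the standard error √(4/63 + 1/31) = 0.309. Power is about 0.90 (0.903 normal, 0.894 Welch t). It has no bearing on IPSS.

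**Inputs for IPSS.**
- From the documents: 100 v 50 randomized (13.2); a missing rate of 25% or more expected for primary and secondary endpoints (13.5), hence about 75 v 37 men; two-sided 5% test.
- Assumed, because the documents are silent: IPSS SD 6 at every time point; correlation rY = 0.7 between each pre-treatment score and the 6-month score; correlation r12 between the two pre-treatment scores, varied.

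**Variance of the change, in units of the IPSS variance.**
- One pre-treatment score: 2(1 − rY) = 2 × 0.3 = 0.60.
- Mean of two: 1 + (1 + r12)/2 − 2rY.

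| r12 | Variance with mean of two | Cut from 0.60 |
|---|---|---|
| 0.70 (all correlations equal) | 0.450 | 25% |
| 0.80 | 0.500 | 16.7% |
| 0.85 | 0.525 | 12.5% |
| 0.90 | 0.550 | 8.3% |
| 0.95 | 0.575 | 4.2% |

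The two pre-treatment scores would be at most about 90 days apart. The 6-month score comes roughly 10 to 12 months after Day 0 (140 days, plus 7 to 14 days, plus 5 to 7 months). The rows with r12 above rY are therefore the more plausible ones.

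**Adjusting for the pre-treatment value (r12 = 0.85, rY = 0.70).**
- Unadjusted change, one score: 0.60.
- Unadjusted change, mean of two: 0.525.
- Adjusted for the screening score alone: 1 − 0.7² = 0.51.
- Adjusted for the mean of two: 1 − 0.49/0.925 = 0.47.

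Adjustment alone cuts the variance by 15% (0.09/0.60). The second score then removes about 8% of what is left (0.04/0.51).

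**Difference detectable with 80% power, unadjusted.** (1.96 + 0.84) × 6 × √variance × √(1/n₁ + 1/n₂):
- 75 v 37 men, one score: 2.80 × 6 × 0.775 × 0.201 = 2.62 points.
- Mean of two, r12 = 0.9: 2.50 points. Mean of two, r12 = 0.7: 2.27 points.
- If only the 10% attrition of section 13.4 applied (90 v 45 men), the three values would be 2.38, 2.28 and 2.06.

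**The case against.** The strongest reply is that nothing here is wrong. Section 7.2 has baseline testing in its title and lists IPSS, so the screening score is a natural reading of baseline. It is also the only score taken before randomization. One pre-treatment questionnaire is a legitimate design, both arms share the schedule under the blind, and LUTS comes last in a prioritized list of exploratory endpoints. All of this stands, and it limits the point to an optional improvement.

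Three further objections also stand. Averaging does not remove an old screening score; it halves its weight. Ninety days is a maximum, and if screening was recent the two scores will agree closely and averaging gains little. Adjusting for the existing screening score needs no new data and, in the 0.85/0.70 case, does better (0.51) than averaging without adjustment (0.525). The fix below therefore includes adjustment, and a second score still adds to it.

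The documents do not support some stronger readings that a reader might infer:
- That the variance would fall by a quarter. This requires scores at most about 90 days apart to correlate no better than scores many months apart.
- That the comparison is biased or the endpoint cannot be computed. The missing visit costs precision only, and the screening score supplies a pre-treatment value.
- That IPSS is the only way urinary symptoms are reported. Participants also record adverse events during the intervention and in the 30-day diary.
- That PSA, measured at both Screening and Baseline, sets a precedent. Screening PSA serves eligibility (4.1.6), and the plan nowhere averages the two values.

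**Conclusion.** The point holds as a cheap gain in precision. The only pre-treatment IPSS is the screening score, up to 90 days old, and the planned test makes no adjustment for it. The comparison between arms remains valid.

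The gain is modest and rests on assumed correlations and an assumed SD. With rY = 0.7, a plausible cut in the variance of the change from averaging is about 4% to 17%; 25% is the equal-correlation limit. Adjustment and a second score together take the variance from 0.60 to 0.47 in the 0.85/0.70 case, a cut of about 22% (0.13/0.60), most of it from the adjustment. The calculation also assumes equal SDs over time and that both pre-treatment scores track the 6-month score equally well. If the later score tracks it better, the gain is larger; if worse, smaller. No conclusion about the primary endpoints is affected.

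**What to change.** 1. In 7.1 and 7.3 (and the matching text in section 3), add IPSS to the Baseline Visit, completed before the first injection.
2. In 8.2.13, define the pre-treatment value as the mean of the Screening and Baseline Visit scores, or the single available score if one is missing.
3. In 13.5, compare the arms on the 6-month IPSS adjusted for that value, in place of the unadjusted t test on change.

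If no visit content can be changed, items 2 and 3 still apply with the screening score named as baseline, and need no new data. Item 3 should be settled before unblinding.

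The cost is a minor amendment, a few minutes per man, and one more copy of a form already used at four time points. The documents give no cost figure. No dose, eligibility rule or clinical care is touched.

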8.3 Off-Agent Criteria

Participants may stop receiving study agent for the following reasons: completed the protocol-prescribed intervention, adverse event or serious adverse event, inadequate agent supply, noncompliance, concomitant medications, or medical contraindication. Participants will continue to be followed, if possible and appropriate, for safety reasons and in order to collect endpoint data according to the schedule of events. Vaccine injections may be held at the discretion of the patient and/or investigator for any concerns related to drug toxicity.

8.4 Off-Study Criteria

Participants may go ‘off-study’ for the following reasons: the protocol intervention and any protocol-required follow-up period is completed, adverse event/serious adverse event, lost to follow-up, non-compliance, concomitant medication, medical contraindication, withdraw consent, death, and determination of ineligibility (including screen failure). Study subjects will be followed for 30 days after the last study dose is given.

8.5 Study Termination

NCI, DCP as the study sponsor has the right to discontinue the study at any time.

9. CORRELATIVE/SPECIAL STUDIES

9.1 Rationale for Methodology Selection

The immunologic response to PROSTVAC® in the target tissue will be evaluated by immunohistochemistry (IHC) to assess the CD8⁺, CD4⁺, and PD-L1 positive cells. Immunohistochemistry

is the best and most validated technique for measuring protein levels of the biomarkers of interest in paraffin-embedded tissue. It allows analyses of relative expression levels of each biomarker and determination of localization of each marker. The study will also explore the potential of assessing immunologic response in the target tissue using multiplex immunofluorescence assay. This will allow for the measurement of multiple protein biomarkers in the same tissue section.

Multi-color flow cytometry analysis will be used to analyze the circulating immune cell subsets. The multi-color flow cytometry is a powerful tool that can separate a heterogenous mixture of cells and has been used in prior trials with PROSTVAC®.

9.2 Comparable Methods

Proposed methods are standard methodologies used in published research studies. The resulting data will be able to be compared to existing data.

10. SPECIMEN MANAGEMENT

10.1 Laboratories

Clinical chemistry, hematology, and PSA will be performed at the institutional or commercial diagnostic laboratories.

[name] laboratory will serve as a central repository for the receipt, storage, and distribution of the tissue sections and serum samples collected from this trial.

The immunohistochemistry analysis (IHC) of immune infiltrates in the prostate biopsies will be performed by the University of Arizona Cancer Center Tissue Acquisition and Cellular/Molecular Analysis Shared Resource under the supervision of [name]. Following the IHC staining of the immune infiltrates, scanned digital images of the de-identified tissue slides will be sent to [name] research group at the NCI for quantitative scoring of the immune infiltrates.

[name] laboratory will serve as the central laboratory for PBMC processing, storage, and distribution.

[name] laboratory at the NCI will perform the 15-Mer prostate specific T-cell assay and the analysis on soluble antibodies to tumor associated antigens.

10.2 Collection and Handling Procedures

Blood Samples

Clinical labs

Approximately 10 ml of blood will be drawn to one 3 ml EDTA and one 7 ml SST or tiger top Vacutainer tubes at screening, Day 84, and at the post intervention for CBC with differentials and CMP. The EDTA tube will be gently inverted to mix for anticoagulation. The SST tube will be held at room temperature for 30 min and then centrifuged. Blood tubes will be prepped, labeled, and packaged according to the recommendations from the diagnostic laboratory.

PSA

Approximately 4 ml of blood will be drawn into one SST or tiger top Vacutainer tube at screening, baseline, Day 84, and at the end of intervention. The SST tube will be held at room temperature for 30 min and then centrifuged. Blood tubes will be prepped, labeled, and packaged according to the recommendations from the diagnostic laboratory.

PBMC

Approximately 60 ml of blood will be drawn into multiple Heparin Vacutainer tubes at baseline and at the end of intervention. The tubes will be labeled with study ID, subject ID, and visit date. The tubes will be gently inverted to mix for anticoagulation and shipped overnight at ambient temperature to a central laboratory for PBMC isolation.

Serum

Approximately 5 ml of blood will be drawn into a SST or tiger top Vacutainer tube at baseline and at the end of intervention. The SST tube will be held at room temperature for 30 min and then centrifuged. Serum will be aliquoted evenly into ten cryovials (~200 µl each) and stored at -80°C. The cryovials will be labeled with study ID, subject ID, and visit date.

Tissue Sections

Unstained tissue slides from pre and post intervention prostate biopsies will be requested from each institution's pathology department for measurement of tissue biomarkers. One to two tissue blocks with tumor from pre-intervention biopsy and same number of tissue blocks with tumor from post-intervention biopsy will be selected to cut the tissue slides. If no tumor was present in the post-intervention biopsy, block(s) from the same tissue region as the pre-intervention block(s) with tumor will be selected. Five to 10 unstained slides will be requested from each block.

